7.3 Adverse Events and Serious Adverse Events

Adverse events will be solicited at each assessment (1 week, 4 weeks, 3 months). If an adverse event is identified unsolicited during a treatment session or other contact with research personnel, the event will be recorded and reported as outlined below.

Definitions

Adverse Event (AE)

An adverse event (AE) is any untoward medical occurrence in a subject during participation in the clinical study or with use of the experimental agent being studied. An adverse finding can include a sign, symptom, abnormal assessment (laboratory test value, vital signs, electrocardiogram finding, etc.), or any combination of these regardless of relationship to participation in the study.

Unanticipated Problems (UP)

The Office for Human Research Protections (OHRP) considers unanticipated problems involving risks to subjects or others to include, in general, any incident, experience, or outcome that meets **all** of the following criteria:

- Unexpected in terms of nature, severity, or frequency given (a) the research procedures that are described in the protocol-related documents, such as the IRB-approved research protocol and informed consent document; and (b) the characteristics of the subject population being studied;
- Related or possibly related to participation in the research (“possibly related” means there is a reasonable possibility that the incident, experience, or outcome may have been caused by the procedures involved in the research); and
- Suggests that the research places subjects or others at a greater risk of harm (including physical, psychological, economic, or social harm) than was previously known or recognized.

Serious Adverse Event (SAE)

A serious adverse event (SAE) is one that meets one or more of the following criteria:

- Results in death
- Is life-threatening (places subject at immediate risk of death from the event as it occurred)
- Results in inpatient hospitalization or prolongation of existing hospitalization
- Results in a persistent or significant disability or incapacity
- Results in a congenital anomaly or birth defect

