6. STUDY PROCEDURES

6.1 Schedule of Evaluations

Assessment	Screening Assessment (Day -7 - 0)	Baseline Assessment, Visit 1 (Day 0)	TX Visits 1-2 (Days 0-7)	1 Week Follow-Up (Day 7-10)	TX Visits 3-8 (Days 8 – 35)	4 Week Follow-Up (Day 29-42)	3 Month Follow-Up (Day 83-97)
Informed Consent Form		X					
Eligibility Criteria	X	X					
Demographics		X					
Medical History		X					
Physical Examination		X		X		X	X
Enrollment		X					
Self-Report Questionnaires							
Oswestry Disability Index	X*	X*		X		X	X
Numeric Pain Rating		X		X		X	X
Psychological Covariates (FABQ, PSESF, PCSF)		X		X		X	X
Global Rating of Change						X	X
Spinal Stiffness Assessment			X	X		X	X
Multifidus Assessment			X	X		X	X
Adverse Events/Side Effects				X		X	
Randomization				X			
Treatment Session Form			X		X		

*Oswestry is to be administered once between screening and baseline, or twice if needed at clinician discretion or if > 7 days has passed since first Oswestry completed.

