6.2.4 Follow-up Visits

- Treatment Visits 1 and 2 (*completed within the 7 days following day 0*):
 - Spine stiffness and multifidus activation assessments pre- and post-SMT treatment
 - Treatment Session Form
- 1-Week Assessment (*completed from Day 7 – Day 12*):
 - Physical examination
 - Self-report questionnaires
 - Spine stiffness measures
 - Multifidus activation measures
 - Side effects questionnaire
- Treatment Visits 3 - 8 (*completed from Day 8 – Day 35, no more than 2 sessions/week*):
 - Treatment Session Form
- 4-Week Assessment (*completed from Day 29 – Day 42, 3 weeks after 1-Wk assessment*):
 - Physical examination
 - Self-report questionnaires
 - Spine stiffness measures
 - Multifidus activation measures
 - Side effects questionnaire

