6.2.5 Completion/Final Evaluation

The final evaluation occurs 3 months after Baseline (*from Day 83 – Day 97*). The following assessments are performed at the final evaluation. If a participant wishes to terminate the study early, this is also the list of assessments we will attempt to complete at termination. Early termination will only be done at a participant's request or if a participant's risk-to-benefit ratio is substantially altered due to a change in status.

- Physical examination
- Self-report questionnaires
- Spine stiffness measures
- Multifidus activation measures

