7.4 Reporting Procedures

The site PI at the University of Alberta must immediately report to the University of Utah PI any serious adverse event, whether or not considered study related, and must include an assessment of whether there is a reasonable possibility that the study caused the event within 72 hours of PI awareness of the event. The site PI for the University of Alberta must also report any unanticipated problems within the same timeframe. The Site PI must also report any other adverse events within 7 days of PI awareness. Participating centers must submit all reports to their local IRB other entities using the following timeline:

- Unanticipated problems that are serious adverse events will be reported to the IRB, DSM committee and NCCIH within 3 days of the investigator becoming aware of the event.

- Other unanticipated problem will be reported to the IRB, DSM committee, and NCCIH within 7 days of the investigator becoming aware of the problem.

Should an unanticipated problem need to be reported to the IRB it will be reported to the IRB of both the University of Utah and University of Alberta. A record of all reportable unanticipated problems will be maintained at the coordinating site and reported during annual DSM reports. In addition, researchers will record at each study visit the occurrence of any other adverse events (e.g., visiting the emergency room or medical provider for pain exacerbation, etc.) A report of all adverse events will be maintained by each site and reported annually on the DSM report.

Characteristics of an Adverse Event

Relationship to Study Intervention

To assess relationship of an event to study intervention, the following guidelines are used:

1. Related (Possible, Probable, Definite)
 - a. The event is known to occur with the study intervention.
 - b. There is a temporal relationship between the intervention and event onset.
 - c. The event abates when the intervention is discontinued.
 - d. The event reappears upon a re-challenge with the intervention.
2. Not Related (Unlikely, Not Related)
 - a. There is no temporal relationship between the intervention and event onset.
 - b. An alternate etiology has been established.

Expectedness of SAEs

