7.5 Followup for Adverse Events

All adverse events will be followed for outcome information until resolution or stabilization.

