7.6 Safety Monitoring

The scope and the purpose of this study qualifies as a Phase III clinical trial, therefore a data and safety monitoring (DSM) board will be established based on the NIH guidelines and NCCIH input, and commensurate with the level of risk, size, and complexity of this study.

Composition of the DSM: The DSM Board will be composed of three individuals with expertise in disciplines relevant to the conduct of this study who are not involved in the study, and have no conflict of interest or economic interest in the results of the study.

Frequency and Character of DSM Meetings: Because this study involves procedures with minimal risk, we propose to conduct DSM meetings via conference call on an annual basis. Each DSM meeting will begin with an open session that will be attended by all trial Investigators, Study Coordinators and representatives from the NCCIH Program Office. Open session will review study procedures, plans for data and safety monitoring, recruitment and retention, gender and minority inclusion, protocol adherence, data management, the occurrence of any adverse events. The open session will be followed by a closed session that will be attended by only the DSMB members and NCCIH representatives. The closed session will be used to discuss data to which the other Investigators must remain blinded.

Content of DSMB Meeting Reports: DSM report from each meeting will review the topics discussed at the meeting with respect to study procedures, accrual and retention, data management, etc. The DSM report will include a recommendation concerning continuation of the study. Each DSM report will provide a tally of all adverse events in each of the categories listed above in all treatment groups. Blinding of adverse event results will be maintained and will be broken only if the DSMB indicates a need to un-blind groups for serious safety reasons. DSMB reports will be submitted to the Principal Investigator, the NCCIH Program Office, and the University of Utah and University of Alberta Institutional Review Boards.

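### Section 7.3 solicits adverse events at 3 months, but the section 6.1 schedule and the 6.2.5 final and early-termination list contain no item for it

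*Combined protocol and SAP*

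**What the plan says.** The safety sections commit to three solicited time points. Section 7.3 reads "Adverse events will be solicited at each assessment (1 week, 4 weeks, 3 months"), and adds that events learned of in other ways are recorded too. Section 7.4 points the same way: "researchers will record at each study visit the occurrence of any other adverse events".

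The visit sections say something else:

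- In the 6.1 schedule, the row "Adverse Events/Side Effects" is marked at the 1-week and 4-week follow-ups. Its 3-month cell is blank.
- In 6.2.4, the item "Side effects questionnaire" appears under the 1-week and 4-week assessments, as a bullet of its own beside the self-report questionnaires.
- In 6.2.5, the final evaluation consists of physical examination, self-report questionnaires, stiffness measures and multifidus measures. There is no adverse event item. The same section says "If a participant wishes to terminate the study early, this is also the list of assessments we will attempt to complete at termination".

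Section 7.6 sets out how the data are used: "Each DSM report will provide a tally of all adverse events in each of the categories listed above in all treatment groups".

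**The concern.** Staff usually run visits from the schedule and the visit lists, and the protocol text does not say which section prevails. A site using section 6 would not solicit events at 3 months, nor from a participant who stops before the next scheduled questionnaire. Events starting after the 4-week visit would then be captured only if volunteered, or through the general recording duty in 7.4, which has no matching item in the 6.2.5 list.

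At stake is the completeness of the harms data. Events never asked about may not be recoverable later, and two sites working from different sections could collect 3-month events differently. Early stoppers matter most. Under 6.2.5 they leave at their own request or because their balance of risk and benefit has changed, and the questionnaire they miss covers time on treatment.

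**Working it through.** The plan gives no figure to reproduce on this point. The check compares the sections and then sizes the gap from the stated visit windows.

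**Is the mismatch real?**

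| Time point | 7.3 / 7.4 | 6.1 row | 6.2.4 / 6.2.5 lists |
|---|---|---|---|
| 1 week | yes | marked | listed |
| 4 weeks | yes | marked | listed |
| 3 months | yes | blank | not listed |
| Early termination | 7.4 only (any study visit) | no column | not listed |

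The blank cell is not a table-reading artefact. Other rows, such as the Oswestry and spinal stiffness, carry a legible 3-month mark, and the written lists in 6.2.4 and 6.2.5 agree with the blank. The self-report item in 6.2.5 does not cover it either, because 6.2.4 lists the side effects questionnaire separately and 6.1 places the row outside the self-report block.

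**Gap after the 4-week visit.** Inputs: 4-week window Day 29 to 42 and 3-month window Day 83 to 97 (6.1); Phase II treatment ends by "Day 35, no more than 2 sessions/week" (6.2.4).

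- Shortest gap: 83 − 42 = 41 days. Longest: 97 − 29 = 68 days.
- Treatment time inside the gap: max(0, 35 − day of the 4-week visit). The largest value is 35 − 29 = 6 days.
- Largest share of the gap on treatment: 6 / (83 − 29) = 6/54 = 11.1%. At least 88.9% is therefore after treatment, and all of it is if the 4-week visit falls on Day 35 or later. Section 3 treats 4 weeks as the end of Phase II.

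**Early termination.**

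- Stopping before the 1-week visit: up to 2 SMT sessions, over 10 days (6.1 window to Day 10) or 12 days (6.2.4 window to Day 12).
- Stopping between the 1-week and 4-week visits: up to 6 sessions (visits 3 to 8), over 21 days as scheduled (3 weeks) and at most 42 − 7 = 35 days by the windows.
- Number not retained at 4 weeks, from 280 enrolled and the two retention rates in 9.2: 280 × (1 − 0.95) = 14, and 280 × (1 − 0.92) = 22.4, about 22.

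**The case against.** The strongest reply is that section 7 belongs to the same protocol and requires the 3-month solicitation. Section 10.3.1 has all personnel study the protocol and receive instruction in safety monitoring, and the data forms that would show actual practice are not among the documents. That a site would skip the question is therefore an inference. This stands, and if sites follow section 7 the 3-month loss is zero. It does not remove the contradiction or tell staff which section to follow.

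Second, 7.3 names three assessments and no termination visit, so the early-termination part does not contradict 7.3 itself. That is correct. However, 7.4 reaches any study visit, and 6.2.5 ties termination to the same deficient list, so the two are best repaired together.

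Third, the 14 to 22 includes people simply lost to contact, whom a new bullet cannot help. That also stands. The figure is a ceiling, and the documents support no estimate of how many would attend a termination visit.

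Fourth, the impact is small. The procedures are described as minimal risk, the omission is the same in every arm, and most of the gap is after treatment. Known events continue to be tracked ("All adverse events will be followed for outcome information until resolution or stabilization"). The 3-month visit still includes physical examination, Oswestry, pain rating and global rating of change, and section 8 has staff watch for neurologic and red-flag signs at visits. These limits hold, with one qualification: under section 8, participants whose intervention is discontinued give self-report outcomes only, so the physical examination is no safeguard for them.

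Finally, a plain adverse event prompt at 3 months would also satisfy 7.3. Cutting 7.3 back to 1 and 4 weeks would remove its own conflict with 6.1, but would leave 7.4 at odds with section 6 and early stoppers uncovered.

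**Conclusion.** The concern holds. The protocol contradicts itself on whether adverse events are solicited at 3 months, and its early-termination list omits them altogether. If section 6 is followed as written, 41 to 68 days per participant go without solicitation, at most 11% of that on treatment. Early stoppers could have up to 2 sessions uncovered before the 1-week visit, or up to 6 in Phase II. At most 14 to 22 of 280 would be in the Phase II group.

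The sizes rest on the stated windows and retention rates, and on a site working from section 6. The consequence is confined to harms ascertainment and the safety board tally. This should be corrected, but it does not threaten the trial's main conclusions.

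**What to change.** Bring section 6 into line with section 7.3:

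1. In the 6.1 schedule, mark the adverse event row at the 3-month follow-up.
2. In 6.2.5, add the side effects questionnaire, covering the time since the last one completed, so that it applies at the final evaluation and at early termination.

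Nothing else in the design or analysis needs to change. The questionnaire exists and the 3-month visit already takes place, so the burden is a few minutes per participant. The change needs a protocol amendment and IRB approval at both sites. If some participants have already passed 3 months without being asked, the trial report should state how many.

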7.4 Reporting Procedures

The site PI at the University of Alberta must immediately report to the University of Utah PI any serious adverse event, whether or not considered study related, and must include an assessment of whether there is a reasonable possibility that the study caused the event within 72 hours of PI awareness of the event. The site PI for the University of Alberta must also report any unanticipated problems within the same timeframe. The Site PI must also report any other adverse events within 7 days of PI awareness. Participating centers must submit all reports to their local IRB other entities using the following timeline:

- Unanticipated problems that are serious adverse events will be reported to the IRB, DSM committee and NCCIH within 3 days of the investigator becoming aware of the event.

- Other unanticipated problem will be reported to the IRB, DSM committee, and NCCIH within 7 days of the investigator becoming aware of the problem.

Should an unanticipated problem need to be reported to the IRB it will be reported to the IRB of both the University of Utah and University of Alberta. A record of all reportable unanticipated problems will be maintained at the coordinating site and reported during annual DSM reports. In addition, researchers will record at each study visit the occurrence of any other adverse events (e.g., visiting the emergency room or medical provider for pain exacerbation, etc.) A report of all adverse events will be maintained by each site and reported annually on the DSM report.

Characteristics of an Adverse Event

Relationship to Study Intervention

To assess relationship of an event to study intervention, the following guidelines are used:

1. Related (Possible, Probable, Definite)
 - a. The event is known to occur with the study intervention.
 - b. There is a temporal relationship between the intervention and event onset.
 - c. The event abates when the intervention is discontinued.
 - d. The event reappears upon a re-challenge with the intervention.
2. Not Related (Unlikely, Not Related)
 - a. There is no temporal relationship between the intervention and event onset.
 - b. An alternate etiology has been established.

Expectedness of SAEs

The Study PI and investigators will be responsible for determining whether an SAE is expected or unexpected. An adverse event will be considered unexpected if the nature, severity, or frequency of the event is not consistent with the risk information previously described for the intervention.

Severity of Event

The following scale will be used to grade adverse events:

1. Mild: no intervention required; no impact on activities of daily living (ADL)
2. Moderate: minimal, local, or non-invasive intervention indicated; moderate impact on ADL
3. Severe: significant symptoms requiring invasive intervention; subject seeks medical attention, needs major assistance with ADL

7.5 Followup for Adverse Events

All adverse events will be followed for outcome information until resolution or stabilization.

7.6 Safety Monitoring

The scope and the purpose of this study qualifies as a Phase III clinical trial, therefore a data and safety monitoring (DSM) board will be established based on the NIH guidelines and NCCIH input, and commensurate with the level of risk, size, and complexity of this study.

Composition of the DSM: The DSM Board will be composed of three individuals with expertise in disciplines relevant to the conduct of this study who are not involved in the study, and have no conflict of interest or economic interest in the results of the study.

Frequency and Character of DSM Meetings: Because this study involves procedures with minimal risk, we propose to conduct DSM meetings via conference call on an annual basis. Each DSM meeting will begin with an open session that will be attended by all trial Investigators, Study Coordinators and representatives from the NCCIH Program Office. Open session will review study procedures, plans for data and safety monitoring, recruitment and retention, gender and minority inclusion, protocol adherence, data management, the occurrence of any adverse events. The open session will be followed by a closed session that will be attended by only the DSMB members and NCCIH representatives. The closed session will be used to discuss data to which the other Investigators must remain blinded.

Content of DSMB Meeting Reports: DSM report from each meeting will review the topics discussed at the meeting with respect to study procedures, accrual and retention, data management, etc. The DSM report will include a recommendation concerning continuation of the study. Each DSM report will provide a tally of all adverse events in each of the categories listed above in all treatment groups. Blinding of adverse event results will be maintained and will be broken only if the DSMB indicates a need to un-blind groups for serious safety reasons. DSMB reports will be submitted to the Principal Investigator, the NCCIH Program Office, and the University of Utah and University of Alberta Institutional Review Boards.

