We will recruit a total of 316 subjects age 18-60 with non-specific LBP and an Oswestry Disability score of at least 20%. Following Phase I treatment, subjects will be randomized in equal proportions to one of 8 possible treatment combinations in Phase II. Randomization will be stratified by responder status (yes/no) during Phase I.

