9. STATISTICAL CONSIDERATIONS

9.1 General Design Issues

This study uses a factorial design examining 3 intervention components (additional SMT, mobilizing and multifidus activating exercise) provided in 8 different combinations following provision of 2 SMT treatment sessions. All participants will receive 2 SMT sessions. At the third session participants will be categorized as responders or non-responders based on a threshold of 50% improvement on the OSW. Randomization to subsequent treatment is stratified by responder status. We will randomly assign participants to receive 6 additional sessions (or no additional treatment) over 3 weeks with varied combinations of additional SMT and exercise co-interventions. It is important to distinguish the factorial design from an 8-arm trial. The factorial approach evaluates the main effects of the 3 additional intervention components (additional SMT, mobilizing and multifidus activating exercise) and interactions among components. It does not compare 8 distinct treatment arms and thus is more efficient with a smaller sample size relative to an 8-arm randomized trial.

Our primary hypothesis is that one or more combination of treatment components will optimize improvement in SMT mechanistic effects (reduction in spinal stiffness and improvement in multifidus activation) as well as improvement in patient-centered outcomes (LBP-related disability and pain intensity). Our secondary hypothesis is that responder status after 2 sessions will moderate the mechanistic and patient-centered outcomes. Our work and the work of others has demonstrated that these mechanistic and patient-reported outcomes are valid and can be collected reliably.

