9.2 Sample Size and Randomization

Based on our past trials, we project 95% retention at 4-weeks. We estimated standard deviations of each outcome based on patients in a similar project with analogous eligibility criteria, and conservatively estimated pre-post correlations to be 4%-7% smaller than the values in this study. Assuming a sample size of 316, of which 280 meet all eligibility criteria and 92% of enrolled participants are retained to 4 weeks, the table below displays minimum detectable effect sizes for a) main effects of each protocol component, b) pairwise interactions between components, c) comparison of mean outcome between two levels of one component at a fixed level of another component, d) main effects of the 3 components in subgroup analyses involving half the participants, and e) pairwise interactions between 2 components in subgroup analyses with half the participants. This sample size provides at least 80% power to detect the MCID or hypothesized effect sizes for the main effects of each component for all outcomes, and for analyses of main effects in subgroups and conditional comparisons for each outcome except global stiffness. Power is more limited for secondary aims, such as pairwise interactions within subgroups.

	Assumptions for Outcome Measures in Project			
	Global Stiffness (N)	Multifidus Activation (mm)	Oswestry	Numeric Pain Rating
Assumption				
Mean (SD)	5.55 (1.60)	2.60 (0.124)	24.3 (14.9)	5.06 (2.12)
Pre-post score correlation	0.80	0.70	0.70	0.45
MCID or hypothesized effect size from past work	0.40	0.074	6.0	2.0
Type of effect	Detectable Effect Size			
Main effect	0.37	0.034	4.12	0.76
Pairwise interaction	0.74	0.064	8.24	1.53
Conditional comparison	0.53	0.045	5.83	1.08
Main effect in 50% of subjects	0.53	0.045	5.83	1.08
Interaction in 50% of subjects	1.05	0.091	11.65	2.16

Table. Assumptions and detectable effect sizes informing sample size for the project.

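### The only planned adverse event summary is a tally over treatment groups; no table by component is planned, although the trial is designed to choose among components

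*Combined protocol and SAP*

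**What the plan says.** **Safety summary.** Section 7.6 describes an annual report to the monitoring board: "Each DSM report will provide a tally of all adverse events in each of the categories listed above in all treatment groups". It adds: "Blinding of adverse event results will be maintained and will be broken only if the DSMB indicates a need to un-blind groups". The closed session is limited to board members and funder representatives, but the board's reports also go to the Principal Investigator. No other section defines a summary or analysis of adverse events, and Section 9.4 sets no stopping rules.

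**Design.** The Précis says that "subjects will be randomized in equal proportions to one of 8 possible treatment combinations in Phase II". Section 9.1 says of the factorial approach: "It does not compare 8 distinct treatment arms and thus is more efficient with a smaller sample size". Section 9.6 specifies main effects and interactions of the three components for stiffness, multifidus activation, Oswestry and pain rating only.

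**Collection of events.** Section 7.3 says: "Adverse events will be solicited at each assessment (1 week, 4 weeks, 3 months"). It continues: "If an adverse event is identified unsolicited during a treatment session or other contact with research personnel, the event will be recorded and reported". Section 7.4 puts all adverse events into the annual report and does not separate them by how they were found. Under Section 3, randomized participants receive six further sessions or no further treatment, and Section 6.2.2.3 places randomization at the 1-week assessment.

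**The concern.** The sample was sized so that each component is judged on roughly half the participants against the other half. That pooling is planned for efficacy but not for harm. A reader of the safety tally would see either a single total or eight small masked groups, and would have to know which four groups share a component before the counts could be combined.

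The decision at the end of the trial is which components to keep. Section 7 lists increased back or spine pain, muscle soreness and muscle spasm as expected events, and these could plausibly differ between additional manipulation and the two exercise types. A recommendation built on component-level benefit should have component-level harm beside it.

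A second, smaller issue concerns how events are found. Seven of the eight groups have six extra sessions at which a participant can volunteer an event, and one group has none. Counts that mix volunteered and solicited events therefore partly reflect contact.

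**Working it through.** **1. Sizes.** Section 9.2 gives the enrolled number: "Assuming a sample size of 316, of which 280 meet all eligibility criteria and 92% of enrolled participants are retained to 4 weeks". With eight equal groups, 280/8 = 35 per group. Each component is present in four groups and absent in four, so 280/2 = 140 per level.

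**2. The plan's own use of the margins.** The documents give no event rate, safety power or safety threshold to reproduce. The nearest stated figure is the detectable Oswestry main effect of 4.12 points in Section 9.2. Inputs: SD 14.9, correlation 0.70, N = 280 × 0.92 = 257.6, two-sided alpha 0.025, power 80%.

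Detectable difference = (2.241 + 0.842) × 2 × 14.9 × √(1 − 0.70²) / √257.6 = 4.09.

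This agrees closely with 4.12 and confirms that efficacy is sized on half against half, not on group against group.

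**3. Gain in precision for adverse events.** For risks p₁ and p₂ with n per side, SE = √{[p₁(1 − p₁) + p₂(1 − p₂)]/n}. Moving from n = 35 to n = 140 divides the SE by √(140/35) = 2, whatever the risks.

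Illustrative power = P(Z > 1.96 − difference/SE), two-sided 0.05. All event risks are assumptions.

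| Assumed risks | SE, 35 v 35 | Power | SE, 140 v 140 | Power |
|---|---|---|---|---|
| 10% v 20% | 0.0845 | 22% | 0.0423 | 66% |
| 5% v 15% | 0.0707 | 29% | 0.0354 | 81% |
| 15% v 30% | 0.0982 | 33% | 0.0491 | 86% |
| 1% v 3% | 0.0334 | 9% | 0.0167 | 22% |

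Fisher's exact test gives lower power with the same gap: for 10% v 20%, 13% against 59%.

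Annual reports before full accrual have fewer people. At half accrual (17.5 v 17.5 against 70 v 70), the 10% v 20% case has SE 0.1195 and 0.0598, and power 13% and 39%. The halving of the SE remains.

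**4. Unequal contact.** Each treated group has six sessions after randomization and the no-further-treatment group has none. With a component present, all four groups have six sessions, mean 6. With it absent, three groups have six and one has none: (3 × 6 + 0)/4 = 4.5.

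Suppose true risk is equal, 10% have an event found by solicitation, and 1% to 3% volunteer one per session (both assumed). Recorded risk in a treated group is 1 − 0.90 × (1 − v)⁶, which is 15.3% at v = 1% and 25.0% at v = 3%. Against 10% in the untreated group, the false excess is 5 to 15 points. With a component absent, the recorded risk is 0.75 × 15.3% + 0.25 × 10% = 14.0%, up to 0.75 × 25.0% + 0.25 × 10% = 21.3%. The false excess by component is therefore 1 to 4 points.

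**5. Timing of solicitation.** The 1-week events arise before assignment and carry no information on components. Section 7.3 includes 3 months among the solicited assessments, but the schedule in Section 6.1 marks adverse events at 1 and 4 weeks only, and the final evaluation in Section 6.2.5 lists no side effects questionnaire. If the schedule is followed, events after the 4-week visit rest on unsolicited reports.

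**The case against.** **The data are not lost.** If the tally is listed by group, component margins are sums of four cells, and the board can ask for labels. This stands: it is a reporting gap. But the plan does not call for the sums, the labels are masked by default, and unblinding is reserved for serious safety reasons. Coded component margins avoid that step. If the tally is pooled, there is nothing to sum.

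**The power contrast describes a test nobody proposes.** Also correct. Section 7.6 describes a count and Section 9.4 a judgement on serious events; no passage says two groups will be tested against each other. The power figures only illustrate the gain in precision, and they assume event rates and, in the table, full accrual.

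**Events may be rare.** Section 5.1 reports no adverse events in earlier use of these techniques, and Section 7.2 calls the risk minimal. At 1% v 3% the component table reaches only 22%. This limits the gain for rare events, not for common ones such as soreness.

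**Pain is already analysed by component.** A lasting worsening would show in the pain rating or Oswestry at 4 weeks or 3 months. Transient flares, soreness and spasm would not necessarily.

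**Stronger readings that the documents do not support.** A reader might infer that the board is the only check on harm. It is not: funder representatives attend the closed session and share the safety review, and the board may ask for more frequent reviews (Section 10.3.2). A reader might also infer that volunteered events conceal a harmful component. Their main effect is a false excess over the one untreated group, and it is small at component level.

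**Conclusion.** The point holds as a gap in safety reporting that is cheap to close. Under either reading of the tally sentence, the plan contains no adverse event comparison on the scale at which the trial will make its decision. Component margins halve the standard error of a risk difference relative to a two-group look. That ratio needs only equal allocation; the power figures rest on assumed risks and are illustrative.

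The documents do not support the inference that harm would go unseen, or that the plan analyses safety as an eight-arm trial. Even with the change, a doubling from 10% would be detected only about two times in three at full accrual, and rare serious events would remain hard to detect. The contact imbalance is a reason to show the source of events; it is not evidence of a large bias in component comparisons.

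**What to change.** 1. Keep the group tally and state whether it is pooled or listed by group.
2. In the closed-session report and the final report, add a table of post-randomization adverse events for each component, present v absent (additional SMT, multifidus exercise, mobilizing exercise), with risk differences and confidence intervals. Use coded component labels for the board. Keep the table out of the reports sent to the Principal Investigator, so that the blinding in Section 7.6 is preserved.
3. Show events from the 1-week assessment or earlier separately, as pre-randomization.
4. Show solicited and unsolicited events in separate rows and report both. Keep all serious events in the comparison however they were found: restricting it to solicited events would drop serious events volunteered elsewhere.
5. Reconcile Section 7.3 with Sections 6.1 and 6.2.5 on whether adverse events are solicited at 3 months.

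The table uses data already planned for collection, provided that the source and date of each event are recorded. The cost is extra programming and a table that is less simple to read.
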